Harms will be assessed by monitoring changes in weight, eGFR, CBC, clinic BP, and ABPM. For more definitive assessments, including hospitalizations, serious adverse events will be properly completed and sent to the VAMC DMC as requested. Safety of continued participation will be assessed at each study visit. The stop-points will be treatment-emergent severe adverse events that precludes further exposure to the drug, such as an allergic drug reaction, initiation of renal replacement therapy, or death. If the study drug is stopped, the subject will be continued to be studied so as to not violate the intention-to-treat principle.

Participants

Inclusion Criteria

- Stage 3 or 4 CKD defined as eGFR <60mL/min/1.73m² for ≥3 months or persistent albuminuria for ≥3 months; (i) urine albumin to creatinine ratio of more than 30 mg/g; (ii) urine protein to creatinine ratio of more than 150 mg/g; or (iii) at least 1+ dipstick positive proteinuria. ⁸⁸
- 24h ABPM <140/90 mmHg at baseline in the presence or absence of antihypertensive treatment.
- Hgb between 8 and 10 g/dL.
- No treatment with ESA within the previous 3 months.
- Adults, age 18 and older.

Exclusion Criteria

- Need for packed RBC transfusion in the previous 2 months.
- Myocardial infarction, stroke, or hospitalization for heart failure in the past 2 months.
- In the assessment of the investigator, have hematologic, inflammatory, infectious, or other conditions that might interfere with the erythropoietic response.

Retention of Participants

For half of the participants, only 7 visits are needed. For the others, at least 11 visits over 24 weeks of the trial are needed. We will offer \$20 per visit for participation in the trial to offset travel and time costs.

METHODS

Method of Randomization

Participants will be randomized in a 1:1 ratio to either early or delayed treatment (“waitlisted group”) with EPO according to UACR strata. A random permuted block design will be used to avoid imbalance in assignment to the treatment groups over time. A randomization sequence will be generated by the statistician and individually concealed in sequentially numbered opaque envelopes. After confirming eligibility with the principal investigator, the study pharmacist will dispense EPO according to the randomization sequence.

Measurement of clinic BP

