2. Change from baseline to 12 weeks in systolic BP in the comparisons above. Between group change in hypertension status from baseline to 12 weeks. Worsening of hypertension at any time point will be defined either as an increase in BP medication or an increase in seated clinic diastolic BP of ≥ 10 mmHg or systolic BP ≥ 20 mmHg. Within-group change in hypertension status from 12w to 24 w will be compared to the control period of 0 to 12w in the delayed start group.
3. The primary outcome variable in this aim is to examine the change in FMD from baseline to 4 weeks in those treated with EPO compared to the waitlisted group. The hypothesis being tested is that EPO will cause impairment in endothelial function. Accordingly, those on EPO will have worsening of FMD.
4. The primary outcome variable in this aim is to examine the predictors of change in FMD from baseline to 4 w in those treated with EPO compared to time controls. Predictors of this change will be baseline values of the following variables: ADMA, urine nitrate and nitrite, renin, aldosterone, and plasma endothelin-1 and change from baseline to 4 w in the above variables. This analysis will answer the question: which of the pathways independently is predictive of endothelial dysfunction?

Sample Size

The primary objective of the study is to assess the change from baseline to 12 weeks in diastolic BP in EPO treated patients compared to controls. In the waitlisted group, we will measure the change from 12 weeks to 24 weeks compared to the change from 0 to 12 weeks. We have measured 24h

ambulatory BP in 183 CKD patients 4 weeks apart. The mean diastolic BP at baseline was 68.3 mmHg and at 4 weeks 68.1 mmHg. The mean difference was 0.14 mmHg and the standard deviation of the difference was 10.3 mmHg. With these assumptions, two-tailed tests and 80% power, the required sample size to detect a between-group difference of 5 mmHg is 68 subjects completing the study in each group. Assuming 85% of those randomized complete the trial, we would need to randomize $68/0.85 = 80$ subjects per group, or 160 subjects in total.

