Comparison of the cohort with these measurements will also be done to understand if the inferences based on the ambulatory BPs accurately reflect the differences between the treatment groups using the clinic BPs. Repeated measures mixed models (PROC MIXED in SAS) will be utilized to assess the overall differences between the treatment groups using the clinic BPs. Additional analyses will explore the nocturnal patterns between the groups in the ambulatory BPs as well as the pattern over time using circadian models of BP in each group.

Between-group changes in hypertension status from baseline to 12 weeks will be tested using logistic regression. Worsening of hypertension at any time point will be defined either as an increase in BP medication or an increase in seated clinic diastolic BP of ≥ 10 mmHg or systolic BP ≥ 20 mmHg. The McNemar test will be used to compare within-group change in hypertension status from 12w to 24 w to that in the control period of 0 to 12w.

To test the hypothesis that EPO is causal to EIH via worsening of FMD, we will evaluate changes from baseline in FMD. That is, we will test if the worsening is a mediation effect using the technique described by Judd and Kenny⁹⁶ and elaborated by MacKinnon⁹⁷. The technique, expanded here for more than one potential mediator employs three regression equations:

- A. $Y = \beta_0 + \tau X_p + \varepsilon$
- B. $X_i = \beta_0 + \alpha_i X_p + \varepsilon$
- C. $Y = \beta_0 + \tau' X_p + \beta_1 X_1 + \dots + \beta_i X_i + \dots + \beta_k X_k + \varepsilon$ for all mediators together,
or $Y = \beta_0 + \tau' X_p + \beta_i X_i \varepsilon$ for each mediator separately

Y is the outcome result (e.g., change in 24-hour diastolic systolic BP), X_p is the group (early vs delayed start) and X_i represent the k purported mediators. The total effect of the treatment on the outcome (measured by the coefficient, τ) is the sum of direct effect (τ') of the treatment and the mediated, or indirect, effects ($\alpha_i \beta_i$). Mediation is established when four conclusions are met: (1) the treatment predicts the outcome variable (supported by a test of statistical significance of τ in equation [A]); (2) the treatment causes the potential mediator (α_i is significant in [B]); (3) the mediator causes the

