outcome variable controlling for the group assignment (β_i is significant in [C] and $\tau' < \tau$, which provides evidence for mediation rather than suppression); and (4) the mediated effect is statistically significant. For mediators that satisfy conclusions 1 through 3, the significance of mediation (conclusion 4) will be determined via interval estimation of the mediated effect using the asymptotic variance derivation of Sobel ⁹⁸ since the outcomes are the continuous measures. Additional analyses that look at thresholds of change (binary: worsening of hypertension or not) will utilize bootstrapping methods and logistic regression. The proportion of the effect mediated is calculated as the ratio of the indirect effect to the total effect, or $\alpha\beta/\tau$.

The primary outcome for flow-mediated dilatation is change in FMD from baseline to 4 w in those treated with EPO compared to time controls. Predictors of this change will be baseline values of the following biomarkers: plasma ADMA, urine nitrate and nitrite, and plasma renin, aldosterone, and endothelin-1 and change from baseline to 4 w in the above biomarkers. In addition, the baseline FMD will be an independent variable. This analysis will use regression models similar to the above-listed analyses.

Pre-specified sub-group analyses for BP response

- Effect of age: The effect of age (e.g., 65 or more and <65) will be tested using interaction effects.
- Effect of volume overload: Volume overloaded subjects are more likely to show worsening EIH with EPO therapy. In people with volume overload, renin and aldosterone levels are expected to be low and 24-hour urine Na high. We will dichotomize the baseline levels of these markers and examine the outcome on ambulatory BP using interaction effects.

Safety analysis

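### The Sobel interval for FMD mediation of the BP rise is conservative; a bootstrap or product-distribution interval would recover up to about 21 points of power at no data cost

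*Combined protocol and SAP*

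**What the plan says.** The mediation procedure is in the Combined protocol and SAP, Statistical Methods, in the paragraphs that follow the missing-data text. It fits three regressions: outcome on group (coefficient τ), mediator on group (α), and outcome on group and mediator (τ′ and β). The rule opens: "Mediation is established when four conclusions are met: (1) the treatment predicts the outcome variable". The second conclusion is that α is significant. The third is that β is significant with τ′ below τ. Only mediators that pass these three go on to the fourth, an interval for the mediated effect "using the asymptotic variance derivation of Sobel". The reason given is that the outcomes are continuous. Bootstrapping is planned only for the additional analyses of a binary outcome (worsening of hypertension or not).

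The Sample Size section sizes the trial for the diastolic BP comparison, two-sided with 80% power, and concludes that "the required sample size to detect a between-group difference of 5 mmHg is 68 subjects completing the study in each group". It gives no power for the mediation test, no expected relation between FMD and BP, and no expected proportion mediated.

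**The concern.** The indirect effect is αβ. The sampling distribution of a product of two estimates is skewed unless at least one of them is very precise relative to its size. A symmetric interval of ±1.96 standard errors then reaches zero too often. A continuous outcome does not cure this, so the reason given does not support the choice. The plan already names a method that avoids the problem, but only for the binary outcome.

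The Hypothesis section links the BP rise to worsening endothelial function, and the trial is described as one to understand mechanism. If the mediation rule often misses a real indirect effect, a negative result could be misread as evidence against the endothelial pathway.

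**Working it through.** Here α and β are path coefficients; the significance level is called the 5% level.

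**Inputs from the documents**
- 68 completers per group (Sample Size); allocation 1:1: "Participants will be randomized in a 1:1 ratio" (Method of Randomization).
- τ = 5 mmHg; for diastolic BP change, "the standard deviation of the difference was 10.3 mmHg" (Sample Size).
- FMD effect 0.45% and SD of FMD change 0.93% (Sample Size). The section on measuring endothelial dysfunction calls 0.93% a within-subject SD. On that reading the SD of a change is 0.93 × √2 = 1.32%, used as a sensitivity value.

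**Assumed, because the documents do not give them**
- Two-sided 5% level.
- Path β, set through a within-group correlation r between FMD change and BP change: β = r × 10.3/0.93, so r = 0.1 to 0.6 is about 1.1 to 6.6 mmHg per 1% FMD.
- One mediator, normal errors, complete data.

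**Reproducing the plan's figures**
- n = 2 × (1.96 + 0.84)² × 10.3²/5² = 67 per group; the t-based calculation gives 67.6, so 68. Then 68/0.85 = 80 ("Assuming 85% of those randomized complete the trial"). Power at 68 is about 80%.
- Detectable FMD difference = 2.80 × 0.93 × √(2/68) = 0.447%, matching 0.45%.

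**Why Sobel is conservative: one case by hand**

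The Sobel statistic is αβ/√(α²·SE_β² + β²·SE_α²), which equals z_α·z_β/√(z_α² + z_β²). It is always smaller than the lesser of the two path z-values. At the design values:
- z_α = (0.45/0.93) × √(68/2) = 0.484 × 5.83 = 2.82. Power for this path is Φ(2.82 − 1.96) = 0.80.
- z_β at r = 0.25 is 0.25 × √133/√(1 − 0.0625) = 2.98. Power is Φ(2.98 − 1.96) = 0.85.
- Expected Sobel z = 2.82 × 2.98/√(2.82² + 2.98²) = 8.40/4.10 = 2.05.

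Both paths are significant together in about 0.80 × 0.85 = 68% of trials. The Sobel statistic is centred only just above 1.96, so it succeeds in roughly half.

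**Simulation at the design values** (3,000-6,000 trials per row; mediated share = 0.45 × β/5)

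| r | Share mediated | Planned rule | Sobel alone | Product interval, conclusions 1-3 kept | Product interval alone |
|---|---|---|---|---|---|
| 0.10 | 10% | 6% | – | – | 16% |
| 0.15 | 15% | 14% | 16% | 25% | 32% |
| 0.20 | 20% | 25% | 30% | 40% | 50% |
| 0.25 | 25% | 39% | 46% | 54% | 66% |
| 0.30 | 30% | 51% | 60% | 62% | 75% |
| 0.40 | 40% | 63% | 74% | 67% | 80% |
| 0.50 | 50% | 67% | – | – | 80% |
| 0.60 | 60% | 68% | – | – | 80% |

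Repeated runs at r = 0.25 gave about 45% for Sobel alone and 63-66% for the product interval. A percentile bootstrap (1,000 resamples) gave 47%, 76% and 81% at r = 0.2, 0.3 and 0.4, in line with the product interval.

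**Splitting the loss**
- Sobel against the product interval, neither with preconditions: about 10 points at r = 0.10, a peak of about 21 at 0.20-0.25, about 6 at 0.40, 3 at 0.50, and 0 when the paths are strong.
- The rest comes from requiring τ to be significant, which caps power near 80%.
- Conclusion 2 and the significance part of conclusion 3 add almost nothing to Sobel, because a significant Sobel z already implies that both path z-values exceed 1.96.

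**Sensitivity of the full-rule loss**
- FMD change SD 1.32%: 6, 19, 21, 19, 13, 8 and 6 points at r = 0.1, 0.2, 0.25, 0.3, 0.4, 0.5 and 0.6.
- FMD effect 1.0-1.5%: 6 to 20 points, at most about 5 of them due to Sobel.
- τ = 4 mmHg: 22 to 36 points; τ = 8 mmHg: 6 to 21 points.
- All 80 per group analysed, r = 0.15-0.40: 13 to 25 points.

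**False positives with exactly one path zero:** planned rule 0.3-1.0%, Sobel alone 0.8-2.0%, product interval 3.5-4.8%. A separate run over other settings gave about 1-5% for Sobel and 4-5.4% for the product interval.

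**The case against.** The strongest reply is that this is a secondary, unpowered analysis whose method errs towards under-claiming. Mediation is not among the four items under Outcome Variables. The primary BP test and the randomized FMD comparison do not depend on it. All of that stands, and it limits the importance of the point.

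A reader might infer a fixed loss of 20 to 30 points. The documents do not support that, because the figure depends on path β, which they never state, and on the FMD SD. For example, with an FMD effect of 0.7% and 2 mmHg per 1% FMD, the planned rule and the product interval alone have 47% and 75% power if the SD is 1.32%. With the stated 0.93% they have 37% and 55%, a gap of 18 points.

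A reader might also blame Sobel for the whole gap, or call the τ condition an error. Neither follows. Part of the gap is the τ condition, and requiring a demonstrated BP effect before declaring its mediation is consistent with the plan's hypothesis that EPO causes hypertension through FMD. It also protects the planned ratio αβ/τ, which is unstable when τ is near zero. Statisticians can differ on that condition.

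Finally, the third conclusion contains more than a significance test: τ′ < τ guards against suppression, and a two-sided interval without it could count a wrong-direction effect as mediation. That part should stay.

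**Conclusion.** The point holds for the interval. Sobel is conservative here and costs about 0 to 21 points of power at the plan's design values, depending on an FMD-BP correlation that has to be assumed (0.1 to 0.6). The full rule costs about 10 to 28 points against a product interval without preconditions, and as little as 6 if the FMD change SD is 1.32%. In every setting computed the planned rule had less power than that interval. The alternative rejects at about the nominal 5% or below when there is no mediation, so the gain is not bought with excess false positives. The figures rest on a single mediator, normal errors, complete data and a 5% level; fitting several mediators together would change them. Nothing here affects the primary diastolic BP analysis.

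**What to change.** - For continuous outcomes, replace the Sobel interval with a pre-specified percentile-bootstrap or product-distribution 95% interval for αβ.
- Do not require α and β to be separately significant beforehand. Keep the direction condition τ′ < τ. Report α, β and τ with intervals.
- State whether significance of τ remains a precondition, and why. If it stays, the interval change still recovers part of the loss: at r = 0.25, from about 38% to 52-54%.
- State that the mediation test is not powered, so that a negative result is not read as evidence against the pathway.

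The cost is SAP wording before analysis. No extra data or participants are needed, and the bootstrap is already named in the plan.

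### The proportion mediated, αβ/τ, is not limited to the linear models; with the planned logistic regression for worsening of hypertension it overstates the mediated share and can exceed 100%

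*Combined protocol and SAP*

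**What the plan says.** The mediation text is in Statistical Methods, after the missing-data paragraphs of the primary analysis. It sets out equations A to C for an outcome Y, with change in 24-hour BP as the example. X_p is the randomised group, α is the effect of group on the mediator, β the effect of the mediator on Y given group, τ the total effect and τ' the direct effect.

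- **Sum rule.** The total effect τ "is the sum of direct effect" τ' "of the treatment and the mediated, or indirect, effects" αβ.
- **Condition 3.** β must be significant and τ' must be below τ, "which provides evidence for mediation rather than suppression".
- **Interval.** The Sobel variance is used "since the outcomes are the continuous measures".
- **Binary outcome.** "Additional analyses that look at thresholds of change (binary: worsening of hypertension or not) will utilize bootstrapping methods and logistic regression".
- **Share.** In the sentence directly after that one: "The proportion of the effect mediated is calculated as the ratio of the indirect effect to the total effect", that is αβ/τ.

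Worsening of hypertension is defined "either as an increase in BP medication" or as a rise in seated clinic BP of at least 10 mmHg diastolic or 20 mmHg systolic. No expected frequency is given. For the binary outcome the text changes the regression model and the interval method. It names no estimand, no rescaling of coefficients and no exemption from condition 3.

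**The concern.** The identity τ = τ' + αβ holds for least-squares fits to the same patients. It does not carry over to logistic regression. The odds ratio is non-collapsible: adding a mediator that predicts the outcome moves the treatment coefficient away from zero even when no direct effect has changed. The τ of equation A and the τ' and β of equation C are therefore on different scales. Dividing αβ (scale of C) by τ (scale of A) gives a number that is not a proportion. A bootstrap puts an interval around that number but does not change what is estimated.

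The Objectives and Hypothesis section makes mechanism a central aim, and the share of the BP effect carried by endothelial function is a result readers will look for. The error grows with β, so it is largest when the mediator hypothesis is most nearly right.

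**Working it through.** **The plan's own figures.** No figure is given for the mediation analysis, so the sample-size figures were checked first. With "two-tailed tests and 80% power", a 5 mmHg difference, SD 10.3 and a 5% significance level (assumed; not stated): n = 2 × (1.96 + 0.84)² × (10.3/5)² ≈ 67 per group, or 68 with the t distribution, as stated. The detectable FMD difference at 68 per group is (1.96 + 0.84) × 0.93 × √(2/68) = 0.45, also as stated. Relative to its SD that is 0.45/0.93 = 0.48, so a mediator shift near 0.5 SD fits the plan.

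**Linear case.** In a least-squares check on the same subjects, τ and τ' + αβ were both 0.41736. The rules hold there.

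**Logistic case.** Model: logit P(Y=1) = b0 + τ'X + βM, with M = αX + a standard normal error. Write P(x, m) for the risk with treatment set to x and the mediator distributed as in arm m, averaged over M by numerical integration. Then

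- τ (equation A) = logit P(1,1) − logit P(0,0)
- plan's share = αβ/τ
- risk-difference share = [P(1,1) − P(1,0)] / [P(1,1) − P(0,0)]

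Assumed inputs, not in the documents: P(0,0) = 0.35, α = 0.5 SD, β in logits per SD.

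| β | τ' | P(1,1) | P(1,0) | τ | τ' + αβ | αβ/τ | risk-difference share |
|---|---|---|---|---|---|---|---|
| 0.5 | 0.50 | 0.5225 | 0.4636 | 0.709 | 0.750 | 0.35 | 0.34 |
| 1.0 | 0.50 | 0.5523 | 0.4493 | 0.829 | 1.000 | 0.60 | 0.51 |
| 1.0 | 0.25 | 0.5008 | 0.3987 | 0.622 | 0.750 | 0.80 | 0.68 |
| 1.5 | 0.50 | 0.5666 | 0.4347 | 0.887 | 1.250 | 0.85 | 0.61 |
| 1.5 | 0.25 | 0.5227 | 0.3917 | 0.710 | 1.000 | 1.06 | 0.76 |

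Second row in full: αβ/τ = 0.5/0.829 = 0.60; (0.5523 − 0.4493)/(0.5523 − 0.35) = 0.1030/0.2023 = 0.51.

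**Wider grid.** Control risk 5, 20 and 40%, α 0.25 to 0.8, β 0.5 to 2, τ' 0 to 1.5: τ was below τ' + αβ in all 144 combinations. Compared with αβ/(τ' + αβ), the plan's ratio was inflated by about 1 to 6% at β = 0.5, 7 to 21% at β = 1, 17 to 41% at β = 1.5 and 32 to 65% at β = 2. At 5% control risk it often lay within the risk-difference range.

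**Condition τ' < τ.** In large samples it failed despite true mediation in 10 of the 144 combinations, all with α = 0.25 and τ' of at least 1. Example: 20% risk, α = 0.25, β = 2, τ' = 1 gives τ = 0.944, below τ', with about a third of the effect mediated.

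In simulations at 68 per group, among trials with significant τ, α and β, the condition failed as follows:

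- 35% risk, α = 0.5: 2 of 880 (β 1, τ' 0.5), 0 of 556 (β 1, τ' 0.25), 7 of 720 (β 1.5, τ' 0.25).
- 20% risk, τ' = 1: about 6 to 8% (α 0.48, β 1.5), 14% (α 0.25, β 1.5), 24% (α 0.25, β 2).

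**How common the outcome might be.** Assume the ambulatory SDs of change (10.3 diastolic, 16.7 systolic) apply to clinic BP. By chance alone, P(rise ≥ 10) = P(Z ≥ 0.97) = 0.166 and P(rise ≥ 20) = P(Z ≥ 1.20) = 0.116. Either, if independent: 1 − 0.834 × 0.884 = 0.26 at one visit. With a diastolic–systolic correlation of 0.8 it is about 0.20. Medication increases would add to this.

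**The case against.** **The text does not say that the linear rules carry over.** The equations have additive errors, the only example of Y is continuous, and the share sentence can be read as closing the linear framework. This stands in part: the carry-over is read from general wording and placement. But the share sentence directly follows the logistic one, carries no restriction, and no other quantity is offered for the binary outcome. An analyst following the text would compute αβ/τ there.

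**The sizes rest on strong mediators.** β of 1, 1.5 and 2 correspond to latent correlations of about 0.48, 0.64 and 0.74, and the documents give no correlation between FMD and BP. At β = 0.5 the error is negligible. Sampling noise is also wide: at β = 1, τ' = 0.5, the estimated share ranged from 0.19 to 1.05 (95% of trials with significant τ). All of this stands and limits the weight of the point. It does not justify the formula, because noise shrinks with more data and this bias does not.

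**A reader might infer that the trial is likely to discard a true mediator through τ' < τ.** The figures do not support that. With a small shift, such as 0.1 SD, the mediator is mostly lost earlier, at the test of α, for lack of power. With a 0.5 SD shift and moderate direct effects, the wrong failures simulated were under 1%.

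**A reader might also infer that the outcome is known to be common.** No event rate is given, and the 20 to 26% above borrows ambulatory SDs for clinic BP.

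**Conclusion.** The point holds as a defect in how the binary mediation analysis is specified. Applied to logistic fits, αβ/τ overstates the mediated share: trivially at β = 0.5 (0.35 against 0.34), materially at β = 1 (0.60 against 0.51), and badly at β = 1.5 (0.85 against 0.61, or 1.06 against 0.76 with the smaller direct effect). These sizes assume 35% control risk and a 0.5 SD mediator shift; neither the event rate nor β is in the documents.

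The τ' < τ condition is a lesser problem. At 68 per group, wrong failure reaches about 6 to 24% of otherwise passing trials only with β of 1.5 to 2, τ' of 1 and 20% risk.

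The documents do not support reading this as a flaw in the primary diastolic BP comparison, in the sample size or in the continuous-outcome mediation. The point concerns a secondary, mechanistic analysis that should be corrected because the correction is nearly free.

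**What to change.** For worsening of hypertension, replace the product-of-coefficients share with natural direct and indirect effects on the risk-difference scale. Obtain them by regression standardisation from the logistic outcome model and the linear mediator model, and take intervals from the bootstrap already planned. State which indirect effect is reported (treatment held at EPO or at control), since the two differ somewhat. State also the assumption of no unmeasured confounding between mediator and outcome. If a proportion is wanted, take it as indirect over total on that same scale.

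Add one sentence limiting the sum rule, αβ/τ and τ' < τ to the linear models for continuous outcomes.

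The cost is SAP wording and slightly more analysis work with standard mediation software. No extra data or patients are needed.
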